- **Acceptance and Non-Acceptance Summary Reports** - Study Champion can use this filter to look at overall acceptance or non-acceptance of empiric antibiotic recommendations.
 - This summary level report will be available as an initial view of overall acceptance or non-acceptance for (1) clinician-level and (2) hospital-level acceptance (compared to other Arm 2 facilities). It will allow for range filtering for viewing data across designated periods of time that allows trending.
 - This option will be available for viewing/printing summary tables and graphs with de-identified clinician information.
 - This report will be able to be filtered by initial antibiotic ordered.
- **Antibiotic Prescribing Per Protocol** - defined as # (%) of per-protocol antibiotic prescribing among patients with ABD Infections. This gives clinicians credit for choosing standard spectrum antibiotics that never required a trigger in the risk estimate prompt.
- **Emergency Department (ED) ICU-Bound Prompt Report** - INSPIRE CPOE workflow includes a prompt to ED clinicians asking if the patient is ICU-bound. If response is “yes” then no further CPOE screens will fire. This report allows study champions to see how often ED clinicians respond “yes” to assess whether clinicians may be circumventing the prompt.
- **Prompt Report** - This report provides the # or % of opportunities that results in a CPOE risk estimate prompt activation.
 - Allows filtering by prompt action chosen (cancel, override, replace)
- **Override Report** – Some pharmacists may want to be able to filter by type of override for intended follow up plan that day. They may know they are going to round in the ICU, they may want to print out a list of all overrides due to ICU-bound and check to see if they actually went to the ICU while they were there, or they may be doing medication reconciliation with allergies and want a printout of all the overrides due to allergies and cross check those simultaneously.
- **Extended-Spectrum (ES) Indications Report** – For use if Study champion would like to organize by ES antibiotic orders and by indication.

F. Study Schedule

The timeline for the trial is shown in Figure 3 below, with key milestones indicated.

Figure 3. INSPIRE-ASP Trial for Abdominal Infections Timeline: 6/2020 – 5/2025

MILESTONE	Year 1 (6/20 - 5/21)				Year 2 (6/21 - 5/22)				Year 3 (6/22 - 5/23)				Year 4 (6/23 - 5/24)				Year 5 (6/24 - 5/25)			
	Q1	Q2	Q3	Q4																
Facility Recruitment																				
Randomization with Baseline Characteristics																				
Committee Approvals																				
Coaching Calls																				
Site Visits																				
Distribute Toolkit																				
Phase in (5-month)																				
Intervention (12-month)																				
Clinician Feedback Reports																				

G. Assessment of Outcome Measures

G.1. Data Sources and Collection

Trial data will not be collected by participating sites. Instead, all variables and outcomes will be obtained from custom extractions from the HCA Healthcare computerized data warehouse. HCA Healthcare has a long-established corporate data warehouse with admission data, demographics, diagnostic and procedure codes, CPOE data, and laboratory and pharmacy data. Trial data from the computerized data warehouse will include demographic, insurer, comorbidity, and laboratory (including microbiology) data for ABD infection cohorts.

G.2. Specifications of the Appropriate Outcome Measures

The primary, secondary and safety trial outcomes are summarized below in Table 3.

G.3. Primary Outcome Measures

The primary trial outcome for ABD infections reflects the national metric of days of therapy (DOT) of extended-spectrum antibiotic use (ES-DOT), which we will evaluate for the empiric period (hospital day 1-3). Trial success will be based upon the relative reduction in this metric between the INSPIRE Stewardship Bundle vs routine care arm when accounting for baseline values.

G.4. Secondary Outcome Measures

There will be two secondary outcomes for ABD infection (antipseudomonal DOT and vancomycin DOT).

G.5. Safety Outcomes

Two safety outcomes will also be assessed. We will evaluate if increased use of standard-spectrum antibiotics causes increased ICU transfers or hospital length-of-stay.

Table 3. Trial Outcomes

Outcome	Metric for ABD Cohort
Primary Trial Outcome: Total Empiric Extended-Spectrum Antibiotic Days of Therapy (ES-DOT)	The number of different extended-spectrum antibiotics each empiric day, summed across the first 3 days of hospitalization. ¹
Secondary Trial Outcomes: Vancomycin Days of Therapy across Empiric Day and Total Empiric Antipseudomonal Antibiotic Days of	The number of days Vancomycin was received on the first 3 days of hospitalization. ¹
	The number of different antipseudomonal antibiotics each empiric day, summed

Therapy (ES-DOT)	across the first 3 days of hospitalization. ^{1,2}
Safety Outcomes: ICU Transfer and Length-of-Stay	Intensive Care Unit (ICU) Transfer: Days to ICU transfer, from hospital days ≥ 3 and ≤ 14
	Length-of-stay: Days from hospital admission until discharge or hospital day 14, whichever comes first, where admission day is hospital day 1.

¹E.g., if a patient is admitted for 2 days, ES-DOT will be calculated across those 2 days; however if a patient is admitted for 4 days, only the first 3 days will be evaluated.

²Does not include aminoglycosides or fluoroquinolones

H. Statistical Considerations

H.1. Criteria for Discontinuation or Withdrawal

As a pragmatic trial of a quality improvement protocol, follow-up of the analytic cohort will be assured. It will involve the entire hospitalization as recorded in the electronic health record. Drop-outs will not be applicable at the patient level.

Hospitals can withdraw participation at any time. New antibiotic stewardship interventions affecting prescriptions in the empiric period or changes in EMR system that affect antibiotic order entry (e.g., Patient Keeper, Meditech Expanse) will be assessed by the steering committee for possible conflict and withdrawal of participation (for as treated analyses) during the trial. All participating facilities (via the Study Champion) will report any new proposed initiatives via the study email or in response to a standing polling question on every coaching call. Sites will be trained to understand why competing interventions could jeopardize the findings of the study. Should the Steering Committee identify a conflict, we may report back to the Study Champion to request the facility delay implementation of the new initiative until the trial has ended. If the facility is unable to delay implementation, we will conduct an analysis at the end of the trial to assess the impact of interventions on the trial outcomes, or if the impact to the trial is significant, the facility may be asked to drop from the trial (for as treated analysis).

H.2. Study Outcome Measures

See Section G. above.

H.3. Analysis Plan

Primary Statistical Analysis

The primary trial outcome is defined as the summed number of different ES antibiotics received during each empiric day. An empiric day is a day within the first three days of an admission. We define this outcome as the Total Empiric Extended-Spectrum Days of Therapy (ES-DOT). For clarity, the calculation is as follows: we define a DOT for a particular ES antibiotic as a day in which any number of doses of that antibiotic is given. Different ES antibiotics are summed within each empiric day for each patient admission to determine DOT in that at-risk day. Antibiotics given during an associated emergency department visit on the date of hospital admission are counted toward the ES-DOT of the first hospital day.

The main trial results will be based upon as-randomized, unadjusted analyses of admission-level ES-DOT. In contrast to the national DOT measure defined by CDC for hospitals, we define ES-DOT at the individual admission level so that we can perform analyses on individuals.

The trial will be assessed among the cohort of adult admissions who: 1) have administrative claims codes indicating an abdominal infection is present on admission; 2) received any antibiotic within 3 days of admission; and 3) were admitted to a non-ICU location. For admissions initially on a non-ICU floor and transferred to the ICU, analysis will include only admission days on the non-ICU floor within 3 days of admission.

The trial periods are defined as follows: (1) Baseline: January 1, 2019 – December 31, 2019 (12 months); (2) Phase-in: August 2, 2022 – December 31, 2022 (5 months, does not contribute to analysis); (3) Intervention: January 1, 2023 – December 30, 2023 (12 months). The main evaluation of all outcomes will be difference-in-difference between the Intervention and Baseline periods and between study arm. Trial analysis will use a baseline period prior to the arrival of the COVID-19 pandemic since hospital operations and case mix were severely impacted by this pandemic between Winter 2020-Spring, 2022.²⁵⁻²⁹ Although at the time of this

writing (June, 2022), COVID-19 surges continue to occur nationally, clinical operations and patient case mix at most hospitals have largely returned to near pre-pandemic activity in the setting of widespread vaccination and milder virus strains. Phase-In is scheduled for August, 2022 as participating hospitals are in a state of recovery sufficient to launch the trial intervention with pharmacy/physician engagement.

The unit of analysis will be individual admissions. Individuals can contribute more than one admission. The analytic model will be a generalized linear mixed effects model for differences in differences, with random effects accounting for correlation within cluster, period-varying random effects to allow for differences within hospitals between baseline and follow-up, and admission-level random effects to account for correlation within person and hospital, if sufficient data exist. We plan to use a Poisson model for analysis of outcomes as follows:

$$\log(y_{ijph}) = \beta_0 + \beta_1 A_{ijph} + \beta_2 T_{ijph} + \beta_3 A_{ijph}T_{ijph} + b_{0h} + b_{1h}T_{ijph} + g_j + \log(ed_j)$$

where y_{ijph} is the ES-DOT for patient i for admission j in period p at hospital h , and $A_{ijph} = 1$ if hospital h is in the intervention arm and 0 if not, and $T_{ijph} = 1$ if p is the intervention period and 0 if baseline period. The random effects b_{0h} and b_{1h} allow for different baseline mean admission-level ES-DOT for each hospital and each hospital in the intervention period, respectively. Equivalently, they allow for correlation within hospital at different levels at baseline and at follow-up. The random effect g_j allows each patient to have a different mean ES-DOT. Finally, ed_j is the number of empiric days in the admission.

The assessment of trial success will be determined by the significance of the arm by period interaction term β_3 , which assesses whether the log relative rate of the outcome due to being in the intervention arm in the intervention period is different from 0. The exponentiated parameter estimate for β_3 is the estimated relative rate of ES-DOT per at-risk day due to the intervention, relative to the baseline period. For example, if β_3 had a negative value and a p-value <0.05 , we would conclude that the patient-specific CPOE smart prompts generated a benefit over routine care. Exponentiating the parameter value would provide an estimate of the relative reduction due to the intervention in the expected ES-DOT per at-risk day.

The primary trial analysis will use an as-randomized unadjusted model with two-tailed significance set at alpha = 0.05. Secondary outcomes will be assessed using an as-randomized unadjusted model and will include adjustment for multiple comparisons with two-tailed significance set at alpha = 0.025 for the two secondary outcomes.

Subsequent analyses of the primary and secondary outcomes will include both as-treated and adjusted models. Adjusted models will account for individual characteristics such as age, gender, comorbidities, and prior history of MDROs as well as hospital characteristics such as hospital antibiotic resistance. We will also account for seasonality. All adjusters will be determined a priori. These analyses will be reported as point estimates with confidence intervals and without p-values. The reason for including these analyses is to provide additional information related to the trial outcomes for readers to assess the effects of potential confounders. The reason to not include them in a formal multiple comparisons adjustment is because these analyses are non-independent evaluations relative to the as-randomized unadjusted analyses.

We will separately evaluate intervention period effects by arm alone.

Safety Outcomes

Safety outcomes noted in the above table will be assessed in the most conservative manner to identify potential safety issues. Safety outcomes are required because a reduction in ES-DOT might be achieved only by incorrectly withholding ES antibiotics when they were really needed. Each safety outcome will be evaluated for non-inferiority using an as-randomized unadjusted analysis with a one-tailed significance set at alpha = 0.05. Length-of-stay and days to ICU transfer are evaluated within 14 days of admission since empiric antibiotic selection within the first 3 hospital days is not expected to be a main driver of either outcome beyond this time period; evaluation of baseline data also shows that 93% of abdominal patients have length-of-stay equal to or less than 14 days. Analyses planned for these assessments are proportional hazards models with random effects for each hospital and admission. These models are sometimes called frailty or shared frailty models. Because these are safety outcomes, we do not intend to make adjustments for multiple comparisons in testing them, further increasing conservatism.

All analyses will be performed using current versions of SAS (Version 9.4, as of writing, SAS Institute, Cary NC) and/or R (Version 4.0, as of writing).

C.2.11 Power Size/Sample Size Calculations

Power assessment proceeded as follows, using a Monte Carlo approach.²⁵ We used available data to define a baseline period of 1/1/2019-12/31/2019. In a bootstrap procedure, individuals were selected with replacement from within each hospital, once to represent baseline data and separately to represent “intervention period” data. Hospitals were then “randomized” to intervention or control according to multiple parameters, including number of admissions with abdominal infection and ES-DOT. We then modified the outcomes for the bootstrapped individuals in the “intervention” period in the “intervention” arm to reflect the effect of the intervention.²⁹

We assessed power to identify an overall 12.5% relative reduction in ES-DOT. This effect was implemented by reducing the relative empiric days of therapy for each admission which was exposed to the CPOE prompt. The amount of reduction was a uniform random variate between 0.75 and 1. For example, if the bootstrapped patient initially received 8 ES-DOT and was assigned to have a 12.5% reduction, then that admission intervention ES-DOT would be reduced to 7 days ($8*0.875=7$). The reduction of ES-DOT was selected with a lower bound determined by the investigators as the minimal effect achieved that would be clinically meaningful. Using this method, we have $\geq 99.9\%$ (99.6-99.9%) power to detect this effect.

Since adoption of the intervention will be heavily influenced by the ability to demonstrate safety, our study size was based on the power to detect non-inferiority for safety outcomes. We used methods similar to the above to calculate the power to identify at least a one day increase in length-of-stay for 12.5% of patients who had hospitalizations less than 14 days and found the power was 91.5% (CI 89.6-93.2%), where non-inferiority is defined as a hazard ratio no smaller than 0.98. For days to ICU transfer, we estimated the power to detect a 2% increase in transfers to the ICU on hospital day 3 through 14 to be $>99.9\%$ (CI 99.6-99.9%), where non-inferiority is defined as having a hazard ratio no greater than 1.1 (fewer days to ICU results in a hazard ratio above 1).

For completeness, we note that there are other pre-specified outcomes intended for exploratory analysis in secondary papers for the INSPIRE ABD trial in Table 4 below.

Table 4: Secondary Manuscripts - Other Pre-Specified Outcomes

Secondary Manuscripts (other pre-specified secondary exploratory analyses for later manuscripts)	
Inpatient Extended-Spectrum Days of Therapy after the Empiric Period	The number of different ES antibiotics received each day, on hospital days ≥ 4 and ≤ 14 .
Empiric and Total Antibiotic Costs	Empiric and total antibiotic costs during hospitalization
Incidence of Hospital-Onset C. difficile	Hospital-onset C. difficile positive tests (specimen obtained) on hospital days ≥ 4 and ≤ 14 .
Incidence of Hospital-Onset MDRO-positive Cultures	Newly-detected hospital-onset MDRO-positive cultures on hospital days ≥ 4 and ≤ 14 . Includes total MDRO and specific MDRO subsets.

I. Access to Source Data/Documents

To protect the large volume of protected health information required for the INSPIRE-ASP Abdominal Infections Trial, HCA Healthcare will establish a mechanism similar to our previous trials where the study’s programmer analysts gain access to HCA Healthcare data behind the HCA Healthcare firewall. Programmer analysts will receive remote access to an HCA Healthcare web server where requested data will be placed after extraction by HCA Healthcare information technologists. This extraction process will involve replacement of names and medical record numbers with coded identifiers. Programmers will access this virtual machine to clean and analyze data, and to generate summary level output for review with our statistician.

J. Quality Control and Quality Assurance

Monthly data will be accessed by study data analysts from the HCA Healthcare CDW behind their corporate firewall. We anticipate extracting data monthly to be able to validate the data streams. Data stream validation involves initial validation by HCA Healthcare to ensure the integrity of data capture and transfer from individual hospital electronic data systems to the HCA Healthcare corporate centralized data warehouse. This will occur under general HCA Healthcare operations and has a <<1% error rate.

The study programmer analysts will assess each data element for variation within and across hospitals within individual streams. Data cleaning will involve assessing missing data and unusual month-to-month variation in data elements. Data discrepancies will be resolved by revised data extraction methods, particularly those requiring multiple data streams, and by performing quality control checks on the programming code.

K. Subject Confidentiality

K.1. Future Use of Stored Specimens

This study will not include any stored specimens.

K.2. Subject Confidentiality

To protect the large volume of protected health information required for the INSPIRE-ASP Abdominal (ABD)Infections Trial, study programmer analysts will gain access to HCA Healthcare data behind the HCA Healthcare firewall. Programmer analysts will receive remote access to an HCA Healthcare web server where requested data will be placed after extraction by HCA Healthcare information technologists. This extraction process will involve replacement of names and medical record numbers with coded identifiers. Programmers will access this virtual machine to clean and analyze data, and to generate summary level output for review with the study's statistician.

L. Ethics /Protection of Human Subjects

L.1. Centralized Institutional Review Board (IRB) Process and Prior Experience

As a pragmatic cluster-randomized trial of an antibiotic stewardship quality improvement strategy, we will request a minimal risk determination consistent with our prior HCA Healthcare clinical trials. Reasons supporting a minimum risk determination are: 1) the protocol is guideline-concordant, 2) prompts provide risk estimates and recommendations, but does not supplant clinical judgment, 3) evidence suggests that there is time to wait for culture results in non-ICU patients instead of using empiric extended-spectrum antibiotics for uncommon resistant organisms.

Similar to all prior HCA Healthcare clinical trials, the Harvard Pilgrim Health Care (HPHC) IRB will approve a centralized IRB protocol and coordinate reliance agreements with participating hospitals with support from HCA Healthcare's corporate regulatory affairs liaison ([name] MBA, Vice President, Research Compliance and Integrity). In prior trials, IRB approval can be obtained within 2-3 months and the reliance process can occur in a rolling fashion during recruitment, overall requiring an additional 3-4 months.

L.2 Informed Consent Process

Similar to our prior pragmatic trials, we expect that this intervention of a quality improvement strategy for antibiotic stewardship will meet national regulatory standards for waiver of informed consent under the Office of Human Research Protections (OHRP) criteria 45 CFR 46.116(d), 117(c) since 1) trial activities meet minimal risk criteria, 2) the trial randomizes hospitals, not patients, to a quality improvement strategy, 3) the intervention is not designed to supplant physician judgment, but rather provide relevant information to prescribing physicians who will be educated to choose the treatment they deem most clinically appropriate for individual patients, and 4) all assigned activities will be performed according to usual hospital quality improvement procedures outlined by hospital antibiotic stewardship programs. We will also collect attestations from hospital antibiotic stewardship programs stating that they will continue routine antibiotic stewardship efforts.

Literature References

1. Centers for Disease Control and Prevention. Antibiotic Resistant Threats in the United States, 2013. <https://www.cdc.gov/drugresistance/pdf/ar-threats-2013-508.pdf>. Last accessed August 24, 2019.
2. IMS Health. Avoidable Costs in U.S. Healthcare. Danbury, CT: IMS Health; 2013. http://offers.premierinc.com/rs/381-NBB-525/images/Avoidable_Costs_in%20_US_Healthcare-IHII_AvoidableCosts_2013%5B1%5D.pdf. Last accessed August 24, 2019.

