The trial will be assessed among the cohort of adult admissions who: 1) have administrative claims codes indicating an abdominal infection is present on admission; 2) received any antibiotic within 3 days of admission; and 3) were admitted to a non-ICU location.

The rationale for including only the first three days of the admission is that this is when the actual status of the patient with respect to the need for an ES antibiotic is unknown. Bearing this in mind, antibiotics given during an associated emergency department visit on the date of hospital admission are counted toward the ES-DOT of the first hospital day.

The trial baseline period includes January 1, 2019 – December 31, 2019 (12 months). The intervention period includes January 1, 2023 – December 31, 2023 (12 months). The baseline was selected to include time prior to the arrival of the COVID-19 pandemic since hospital operations and case mix were dramatically affected between Winter 2020-Spring, 2022.¹⁻⁴ Although COVID-19 surges have continued to occur, clinical operations and patient case mix at most hospitals have largely returned to near pre-pandemic activity. We considered that a state of pre-pandemic normalcy returned by summer of 2022, and introduced our intervention on August 2, 2022. The period between then and December 31, 2022 is considered a phase-in period and is not used in trial evaluation.

Primary Statistical Analysis

The primary trial outcome is defined as the summed number of different ES antibiotics received during each empiric day, on the patient-admission level. An empiric day is a day within the first three days of an admission. We define this outcome as the Total Empiric Extended-Spectrum Days of Therapy (ES-DOT). For clarity, the calculation is as follows: we define a DOT for a particular ES antibiotic as a day in which any number of doses of that antibiotic is given. Different ES antibiotics are summed within each empiric day for each patient admission to determine DOT in that at-risk day.

The main trial results will be based upon as-randomized, unadjusted analyses of admission-level ES-DOT. We note that the national DOT measure defined by CDC is measured at the hospital level. We define ES-DOT at the individual admission level so that we can perform analyses on individuals.

The main evaluation of all outcomes will be based on the difference in differences between the intervention and baseline periods and between study arms.

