The unit of analysis will be individual admissions. Individual patients can contribute more than one admission. The analytic model will be a generalized linear mixed effects model for differences in differences, with random effects to account for correlation within hospital between period, within hospital within period between patient, and within patient between admission. We plan to use a Poisson model for analysis of outcomes as follows:

$$\log(y_{ijph}) = \beta_0 + \beta_1 A_{ijph} + \beta_2 T_{ijph} + \beta_3 A_{ijph} T_{ijph} + b_{0h} + b_{1h} T_{ijph} + g_j + \log(ed_j)$$

where y_{ijph} is the ES-DOT for patient i for admission j in period p at hospital h , and $A_{ijph} = 1$ if hospital h is in the intervention arm and 0 if not, and $T_{ijph} = 1$ if p is the intervention period and 0 if baseline period. The random effects b_{0h} and b_{1h} allow for different baseline mean admission-level ES-DOT for each hospital and each hospital in the intervention period, respectively. Equivalently, they allow for correlation within hospital at different levels at baseline and at follow-up. The random effect g_j allows each patient to have a different mean ES-DOT. Finally, ed_j is the number of empiric days in the admission. We note that it may not be possible to fit models with the g_j parameter, for various numerical and computational reasons—the most prominent being a relative sparsity of patients with readmissions. If that proves to be the case, we will randomly select one admission per patient and use the model above without that parameter and omitting the j subscript.

The assessment of trial success will be determined by assessing the significance of the arm by period interaction term β_3 , which estimates the log relative rate of the outcome due to being in the intervention arm in the intervention period. The exponentiated parameter estimate for β_3 is the estimated relative rate of ES-DOT per at-risk day due to the intervention, relative to the baseline period. For example, if β_3 had a negative value and a p-value <0.05 , we would conclude that the patient-specific CPOE smart prompts generated a benefit over routine care. Exponentiating the parameter value would provide an estimate of the relative reduction due to the intervention in the expected ES-DOT per at-risk day.

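### The stated 91.5% length-of-stay power appears to include no hospital-by-period variance, and the safety hazard models should state that they fit that term

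*Protocol*

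**What the plan says.** **Power (Protocol C.2.11).** The source data are calendar year 2019. In the bootstrap, "individuals were selected with replacement from within each hospital, once to represent baseline data and separately to represent" the intervention period. Hospitals are then randomised, and outcomes are altered only in the intervention arm's intervention period. On sizing, "our study size was based on the power to detect non-inferiority for safety outcomes". For the first of these outcomes, "We used methods similar to the above to calculate the power to identify at least a one day increase in length-of-stay" in 12.5% of patients with stays under 14 days. The result is 91.5% (CI 89.6 to 93.2%) against a margin of hazard ratio (HR) 0.98. ICU transfer is given as above 99.9% against HR 1.1.

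**Estimand.** Protocol H.3: "The main evaluation of all outcomes will be difference-in-difference between the Intervention and Baseline periods and between study arm". The SAP (Primary Statistical Analysis) agrees: "The main evaluation of all outcomes will be based on the difference in differences between the intervention and baseline periods" and between arms. The baseline year is 2019 and the intervention year is 2023.

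**Primary model.** The Protocol has "period-varying random effects to allow for differences within hospitals between baseline and follow-up", and the equation carries this as b1h·T. The SAP describes "random effects to account for correlation within hospital between period, within hospital within period between patient".

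**Safety models.** The Protocol (H.3, Safety Outcomes) plans "proportional hazards models with random effects for each hospital and admission". The SAP (Safety Outcomes) lists effects for time period as well as hospital and admission. It gives no equation and does not say whether period is within hospital. Both documents test at one-tailed 0.05.

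**The concern.** Stable differences between hospitals cancel in a difference-in-differences. Hospital-specific change between the two periods does not. Drawing both periods from one hospital-year keeps the first kind of variation and sets the second to zero, apart from resampling noise. The real periods are four years apart with the pandemic between them, and the primary model already allows hospitals to change by different amounts.

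Length of stay is the sensitive outcome because its margin is only 2% on the hazard scale, and the drift variance depends on the number of hospital units, not on patients per unit. If the safety model fits the term, the error rate is controlled but power is below the stated figure. If it does not, the interval is too narrow and non-inferiority is declared at the margin more often than 5% of the time.

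The meaning of safety power is also open. C.2.11 speaks both of detecting non-inferiority and of identifying a one-day increase, and these are different quantities.

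**Working it through.** **1. Inputs.** From the documents: margin HR 0.98, so |ln 0.98| = 0.0202; one-sided z = 1.645; 46 units per arm; stated power 91.5% (z = 1.372); about 99,000 patients in the intervention year; 93% with a stay of 14 days or less. Assumed: τ, the SD across units of the change in log hazard between periods, at 0.01, 0.02, 0.03 and 0.05.

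**2. The stated interval.** 89.6 to 93.2% is the exact binomial interval for 915 successes in 1,000 runs (the run count is inferred from this match). It reflects Monte Carlo error only and makes no allowance for drift.

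**3. Reproducing 91.5%.** Events per arm per period: 99,000 × 0.93 / 2 = 46,035.
- Two arms, intervention year only: SE = √(2/46,035) = 0.0066; power at true HR 1 = Φ(0.0202/0.0066 − 1.645) = 92%.
- Four-cell difference-in-differences, assuming 99,000 in each period: SE = √(4/46,035) = 0.0093; power at true HR 1 = 70%.
- Same four-cell SE, detecting the inserted one-day shift. An approximate check with lognormal stays (assumed median 3 to 5 days, 93% at or below 14 days) put that shift at HR 0.973 to 0.977. Power is then 90% to 80%.

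None of these settles what was computed. The 92% match uses a contrast without the baseline period and may be coincidence.

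**4. Does the resampling remove drift?** In an illustrative simulation (92 hospitals, 1,076 exponential stays each) with a true change SD of 0.05, genuine two-period data showed excess variance of about 0.0025 (= 0.05²) in hospital change. Resampling both periods from one year showed about zero.

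**5. Power with the term fitted, starting from 91.5%.** SE0 = d/(1.645 + 1.372), SE = √(SE0² + 2τ²/46), power = Φ(d/SE − 1.645). For showing non-inferiority at HR 1, d = 0.0202 and SE0 = 0.0067. For detecting the shift, d = |ln 0.973| = 0.0274 (SE0 = 0.0091) or d = |ln 0.977| = 0.0233 (SE0 = 0.0077).

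| τ | Non-inferiority at HR 1 | Detecting HR 0.977 | Detecting HR 0.973 |
|---|---|---|---|
| 0.01 | 89.2% | 89.8% | 90.2% |
| 0.02 | 82.0% | 84.4% | 86.4% |
| 0.03 | 71.2% | 75.8% | 79.9% |
| 0.05 | 49.4% | 55.9% | 63.1% |

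**6. False non-inferiority at HR 0.98 with the term omitted.** Rate = Φ(−1.645 × SE0/SE).

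| τ | SE0 = 0.0067 | SE0 = 0.0093 (four-cell) |
|---|---|---|
| 0.01 | 5.8% | 5.4% |
| 0.02 | 8.1% | 6.7% |
| 0.03 | 11.5% | 8.6% |
| 0.05 | 18.7% | 13.6% |

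A cluster-level simulation (92 units, 60,000 runs, SE0 = 0.0067) agrees. Term fitted: power 88.8, 81.4, 70.6 and 49.2%, with false non-inferiority 4.8 to 5.2%. Term omitted: false non-inferiority 5.7, 7.9, 11.4 and 18.9%.

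**The case against.** **The SAP may already have the term.** It is the later document and it added a time-period effect to the safety model. A single random effect on a two-level period shared by all hospitals would do little, and the SAP's primary model sets out period within hospital. That is a plausible reading, and it stands. A reader might infer that the safety models omit the term and that the error rate is inflated. The SAP does not support that. It shows only that the nesting is unstated, so the second table is conditional. The Protocol text does lack the term, and the two documents need to agree.

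**The size rests on an assumed SD.** This stands too. Nothing in the documents places τ within 0.01 to 0.05, so it cannot be inferred that true power is below 80%. The starting point is also unsettled, as step 3 shows. The figures illustrate sensitivity and do not estimate the loss.

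**The length-of-stay method is not spelled out.** That no between-period shift was added is inferred from the cross-reference to the primary method and from the absence of any such step. The fair wording is that the figure appears to exclude this variance.

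**Length of stay did not alone size the trial.** Correct. C.2.11 refers to safety outcomes in the plural and gives no required number of units, and Protocol section D admits qualifying hospitals beyond the calculated size. What can be said is that length of stay has the lower of the two stated safety powers.

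**The intervention year was over before the SAP was dated.** A restated power therefore cannot change enrolment, and low power with the term fitted errs on the cautious side. The model specification still decides whether a non-inferiority claim at a 2% margin keeps its 5% error rate.

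**Conclusion.** The point holds in a limited form. As described, the bootstrap contains no hospital-by-period variance, so 91.5% is an upper figure for a 2019-versus-2023 difference-in-differences, and its interval does not cover drift. This follows from the resampling scheme and does not depend on τ, provided that length of stay was resampled as the primary outcome was.

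The size is illustrative. With the term fitted and 91.5% as the starting point, an SD of 0.01 costs about 1 to 2 points, 0.02 gives about 82 to 86%, 0.03 about 71 to 80% and 0.05 about 49 to 63%, depending on what power means. The inflated error rates in step 6 arise only if the SAP's period effect is not within hospital.

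A reader might extend the point to the primary outcome, but the figures do not support that. At τ = 0.15, with 49,500 admissions per arm per period and an assumed variance/mean² of 1.2, SE = √(4 × 1.2/49,500 + 2 × 0.15²/46) = 0.0328. Against |ln 0.875| = 0.1335, two-sided power is still about 98%. ICU transfer cannot be sized because no transfer rate is given.

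**What to change.** 1. Write out the length-of-stay and ICU-transfer hazard models with arm, period, arm-by-period, a hospital effect and a hospital-by-period random effect (period within hospital), matching the primary model. Make the Protocol and SAP safety sections agree.
2. State whether safety power means the chance of showing non-inferiority at a stated true hazard ratio, or the chance of detecting the inserted one-day shift.
3. Rerun the bootstrap with the planned model and a hospital-level between-period shift over a stated range, and report length-of-stay power across it. Separate warehouse years, where available, can inform the range. Include a higher value as well, because adjacent years may understate change across the pandemic.

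The cost is some simulation on data already held, a less favourable stated power and a wider safety interval. Enrolment and design do not change.
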